- Trial 3 enrolled 177 subjects (59 randomized to secukinumab 300 mg, 59 to secukinumab 150 mg, and 59 to placebo) and assessed safety, tolerability, and usability of secukinumab self-administration via prefilled syringe for 12 weeks. Subjects received subcutaneous treatment at Weeks 0, 1, 2, 3, and 4, followed by the same dose every 4 weeks for up to 12 weeks total.
- Trial 4 enrolled 182 subjects (60 randomized to secukinumab 300 mg, 61 to secukinumab 150 mg, and 61 to placebo) and assessed safety, tolerability, and usability of secukinumab self-administration via Sensoready pen for 12 weeks. Subjects received subcutaneous treatment at Weeks 0, 1, 2, 3, and 4, followed by the same dose every 4 weeks for up to 12 weeks total.

In all trials, the co-primary efficacy variables were the proportion of subjects who achieved a reduction in PASI score of at least 75% (PASI 75) from baseline to Week 12 and treatment success (clear or almost clear) on the Investigator's Global Assessment modified 2011 (IGA mod 2011). Other evaluated outcomes included the proportion of subjects who achieved a reduction in PASI score of at least 90% (PASI 90) from baseline at Week 12, maintenance of efficacy to Week 52, and improvements in itching, pain and scaling at Week 12 based on the Psoriasis Symptom Diary[®].

The PASI is a composite score that takes into consideration both the percentage of body surface area affected and the nature and severity of psoriatic changes within the affected regions (induration, erythema and scaling). The IGA mod 2011 is a 5-category scale including "0 = clear" "1 = almost clear", "2 = mild", "3 = moderate" or "4 = severe" indicating the physician's overall

assessment of the psoriasis severity focusing on induration, erythema and scaling. Treatment success of “clear” or “almost clear” consisted of no signs of psoriasis or normal to pink coloration of lesions, no thickening of the plaque and none to minimal focal scaling.

The results of Trials 1 and 2 are presented in [Table 3-1](#).

Table 3-1 Clinical outcomes at Week 12 in adults with plaque psoriasis in Trials 1 and 2

	Trial 1			Trial 2		
	Secukinumab 300 mg (N=245) n (%)	Secukinumab 150 mg (N=245) n (%)	Placebo (N=248) n (%)	Secukinumab 300 mg (N=327) n (%)	Secukinumab 150 mg (N=327) n (%)	Placebo (N=326) n (%)
PASI 75 response	200 (82)	174 (71)	11 (4)	249 (76)	219 (67)	16 (5)
IGA of clear or almost clear	160 (65)	125 (51)	6 (2)	202 (62)	167 (51)	9 (3)

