The results of Trials 3 and 4 are presented in [Table 3-2](#).

[figure not shown]
Table 3-2 Clinical outcomes at Week 12 in adults with plaque psoriasis in Trials 3 and 4

	Trial 3			Trial 4		
	Secukinumab 300 mg (N=59) n (%)	Secukinumab 150 mg (N=59) n (%)	Placebo (N=59) n (%)	Secukinumab 300 mg (N=60) n (%)	Secukinumab 150 mg (N=61) n (%)	Placebo (N=61) n (%)
PASI 75 response	44 (75)	41 (69)	0 (0)	52 (87)	43 (70)	2 (3)
IGA of clear or almost clear	40 (68)	31 (53)	0 (0)	44 (73)	32 (52)	0 (0)

Examination of age, gender, and race subgroups did not identify differences in response to secukinumab among these subgroups. Based on post-hoc sub-group analyses in subjects with moderate to severe psoriasis, subjects with lower body weight and lower disease severity may achieve an acceptable response with secukinumab 150 mg.

PASI 90 response at Week 12 was achieved with secukinumab 300 mg and 150 mg compared to placebo in 59% (145/245) and 39% (95/245) versus 1% (3/248) of subjects, respectively (Trial 1) and 54% (175/327) and 42% (137/327) versus 2% (5/326) of subjects, respectively (Trial 2). Similar results were seen in Trials 3 and 4.

With continued treatment over 52 weeks, subjects in Trial 1 who were PASI 75 responders at Week 12 maintained their responses in 81% (161/200) of the subjects treated with secukinumab 300 mg and in 72% (126/174) of subjects treated with secukinumab 150 mg. Trial 1 subjects who were clear or almost clear on the IGA at Week 12 also maintained their responses in 74%

(119/160) of subjects treated with secukinumab 300 mg and in 59% (74/125) of subjects treated with secukinumab 150 mg. Similarly in Trial 2, PASI 75 responders maintained their responses in 84% (210/249) of subjects treated with secukinumab 300 mg and in 82% (180/219) of subjects treated with secukinumab 150 mg. Trial 2 subjects who were clear or almost clear on the IGA also maintained their responses in 80% (161/202) of subjects treated with secukinumab 300 mg and in 68% (113/167) of subjects treated with secukinumab 150 mg.

Among the subjects who chose to participate (39%) in assessments of patient reported outcomes, improvements in signs and symptoms related to itching, pain, and scaling, at Week 12 compared to placebo (Trials 1 and 2) were observed using the Psoriasis Symptom Diary[®].

Infections

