5.2 Treatment groups

At Visit 2/Baseline, eligible subjects will be randomized to one of the following two treatment groups in a ratio of 1:1, with approximately 42 subjects per group:

1. **Secukinumab group:** Subjects (or trained caregivers) will self-administer (or administer to the subject) a dose of secukinumab 300 mg s.c. (two injections of the 150 mg prefilled

syringes) once weekly for five weeks (at Randomization, Weeks 1, 2, 3, and 4), followed by dosing every four weeks, starting at Week 8 through Week 48. In order to maintain the blinding during the Double-blind Induction Period, placebo s.c. doses (two injections of the placebo to 150 mg prefilled syringe) will be self-administered by the subjects (or trained caregivers) at Weeks 13, 14 and 15.

2. **Placebo group:** Subjects (or trained caregivers) will self-administer (or administer to the subject) a dose of placebo s.c. (two injections of the placebo prefilled syringes) once weekly for five weeks (at Randomization, Weeks 1, 2, 3, and 4), followed by a dose after four weeks at Week 8.

Beginning at Week 12, all subjects in the placebo group will be switched to treatment with secukinumab 300 mg s.c. Subjects will receive a dose of secukinumab 300 mg s.c. once weekly for five weeks (at Weeks 12, 13, 14, 15, and 16) followed by dosing every four weeks, starting at Week 20 through Week 48.

All subjects who enter the Double-blind Induction Period will self-administer the Week 12 dose following the completion of all assessments scheduled to be performed at Visit 8/Week 12 (Table 6-1).

The treatment groups and dosing frequency are also described in Table 5-1 below.

Table 5-1 Overview of study treatment

Treatment group	DB Treatment Period (Rand – Wk 12 pre-dose)	DB Induction Period (Wk 12 – Wk 15)	OL Treatment Period (Wk 16 – Wk 52)
Secukinumab 300 mg	2x s.c. secukinumab 150 mg injection at Rand, Wks 1, 2, 3, 4 and 8	2x s.c. secukinumab 150 mg injection at Wk 12 2x s.c. secukinumab 150 mg PBO injection at Wks 13, 14 and 15	2x s.c. secukinumab 150 mg injection at Wks 16 - 48
Placebo (PBO)	2x s.c. secukinumab 150 mg PBO injection at Rand, Wks 1, 2, 3, 4 and 8	2x s.c. secukinumab 150 mg injection at Wks 12, 13, 14, and 15	2x s.c. secukinumab 150 mg injection at Wks 16 – 48

DB = Double-blind; OL = Open-label; Rand = Randomization; Wk = Week

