**Table 1-1 Assessment windows for PASI and IGA assessment:**

Analysis Visit	Week	Scheduled Day	Visit Window
Baseline	BSL	1	-28 day to Day 1
Week 4	4	29	Day 2-43
Week 8	8	57	Day 44-71
Week 12	12	85	Day 72-99
Week 16	16	113	Day 100-141
Week 24	24	169	Day 142-197
Week 32	32	225	Day 198-253
Week 40	40	281	Day 254-309
Week 48	48	337	Day 310-351
Week 52	52	365	Day >=352

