#### **2.7.2.2 Psoriasis Area and Severity Index (PASI)**

PASI 75 / 90 / 100 responses will be analyzed at each time point using the Cochran-Mantel-Haenszel test to compare secukinumab and placebo, adjusting for body weight (<90 kg, ≥90 kg) (Stokes, Davis, and Koch, 2012). A 95% confidence interval for the difference between the two treatment groups in the proportion of subjects who are responders will be calculated using the normal approximation to the binomial distribution.

In addition, the PASI responses by visit will be summarized by treatment.

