#### **2.7.2.3 Investigator's Global Assessment (IGA mod 2011)**

IGA mod 2011 (0 or 1) response will be analyzed at each time point using the Cochran-Mantel-Haenszel test to compare secukinumab and placebo, adjusting for body weight (<90 kg, ≥90 kg). A 95% confidence interval for the difference between the two treatment groups in the proportion of subjects who are responders will be calculated using the normal approximation to the binomial distribution. In addition, the IGA mod 2011 responses by visit will be summarized by treatment.

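### The normal-approximation 95% interval for the Week 12 PASI 75 difference, if uncorrected, covers only about 92–93.5% at the response rates the protocol cites, and its lower limit is too high about twice as often as it should be or more

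*SAP*

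**What the plan says.** SAP section 2.7.2.2 assigns the hypothesis test for the PASI responses to a weight-stratified procedure: "PASI 75 / 90 / 100 responses will be analyzed at each time point using the Cochran-Mantel-Haenszel test". The accompanying 95% confidence interval for the difference in proportions of "responders will be calculated using the normal approximation to the binomial distribution". SAP section 2.7.2.3 treats IGA mod 2011 response in the same way: the interval "will be calculated using the normal approximation to the binomial distribution". Protocol section 9.5.1 has the same rule. None of the three places mentions a continuity correction, and SAP section 5.4 gives code or options only for the primary and supportive analyses.

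Protocol section 3.6 supplies reference rates, in Table 3-1 ("Clinical outcomes at Week 12 in adults with plaque psoriasis in Trials 1 and 2"), in Table 3-2 ("Clinical outcomes at Week 12 in adults with plaque psoriasis in Trials 3 and 4") and, for PASI 90, in the text (for example "in 59% (145/245) and 39% (95/245) versus 1% (3/248) of subjects, respectively (Trial 1"). SAP section 3 plans about 42 subjects per arm.

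**The concern.** The Wald interval is unreliable when a proportion is close to 0 or 1 and the sample is small. Here 0–5% on placebo means about 0 to 2 expected responders among 42 (0.05 × 42 = 2.1), while the secukinumab rate is near 80%. With few or no placebo responders, the estimated variance in that arm is close to zero. When the secukinumab rate happens to be high as well, the variance estimate shrinks further, so large observed differences come with intervals that are too narrow. The lower limit then tends to be too high.

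That limit is what a reader takes as the smallest benefit compatible with the data. If it is too high two to three times as often as stated, the interval is not a 95% interval and its error leans in the drug's favour.

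The point is confined to Week 12. SAP Table 1-1 ("Assessment windows for PASI and IGA assessment") shows that PASI and IGA are also analysed at Weeks 4 and 8, but the documents give no rates for those visits. After Week 12 there is no placebo comparison: "Beginning at Week 12, all subjects in the placebo group will be switched to treatment with secukinumab 300 mg s.c". No PASI 100 rates are given either, so no figure is offered for PASI 100.

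**Working it through.** **Sample size.** The documents state no coverage figure beyond the nominal 95%, so the planned size is the figure to reproduce. With a difference of 0.15 and an SD of 0.196 (SAP section 3), the standardised effect is 0.15/0.196 = 0.765. A two-sided t-test at 0.05 has power 0.901 at 37 per arm, which reproduces the 37. Then 37/0.90 = 41.1, rounded up to 42 per arm, or 84 in total.

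**Inputs for the interval.** PASI 75 at Week 12, secukinumab 300 mg v placebo (protocol Tables 3-1 and 3-2):
- Trial 1: 200/245 v 11/248
- Trial 2: 249/327 v 16/326
- Trial 3: 44/59 v 0/59
- Trial 4: 52/60 v 2/61

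Arm sizes of 37–46 are an assumed range. The documents give 37 and 42, the planned total is approximate, and protocol section 5.5.13 lets subjects already in screening enter after the target is met. Averaging over a range is sensible because Wald coverage is a saw-tooth in n.

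**Method.** For each n and each pair of true rates, all outcomes (x1, x2) of two independent binomials are enumerated. The Wald limits are d ± 1.96 × √[p̂1(1 − p̂1)/n + p̂2(1 − p̂2)/n], with d = p̂1 − p̂2. Coverage is the total probability of the outcomes whose interval contains the true difference. The rest splits into lower limit too high and upper limit too low, each nominally 2.5%. The Miettinen-Nurminen interval is evaluated in the same way.

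**PASI 75, equal arms, mean over n = 37–46.** Entries are coverage % (lower limit too high % / upper limit too low %).

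| Rates | Wald | Miettinen-Nurminen |
|---|---|---|
| Trial 1 | 93.1 (5.7 / 1.2) | 95.1 (1.8 / 3.1) |
| Trial 2 | 93.3 (5.2 / 1.5) | 95.1 (1.9 / 2.9) |
| Trial 3 | 93.5 (4.7 / 1.8) | 95.1 (1.8 / 3.1) |
| Trial 4 | 92.2 (6.8 / 1.0) | 95.1 (1.6 / 3.3) |

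- **At the planned 42 per arm**, Trials 1–4: Wald 92.0 (6.8 / 1.2), 92.3 (6.3 / 1.4), 91.3 (6.3 / 2.3), 92.1 (7.1 / 0.8). Miettinen-Nurminen coverage: 95.8, 95.7, 95.0, 94.0.
- **At single sizes within 37–46**, Wald coverage runs from 89.0% to 95.4% and the lower-limit error from 3.2% to 9.9%.
- **Unequal arms**, all 100 pairs of sizes from 37–46: mean Wald coverage 92.9, 93.3, 93.5, 91.8.

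**Other endpoints, Wald, mean over 37–46.**
- IGA 0/1, Trials 1–4: coverage 93.7–94.0%, lower limit too high 3.8–4.5%.
- PASI 90, Trials 1–2: coverage 93.9–94.1%, lower limit too high 3.2–3.6%.

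**If a continuity correction is applied.** PASI 75 mean coverage is 96.4, 96.6, 96.8 and 96.1% for Trials 1–4, with the lower limit too high in 3.1, 2.8, 2.5 and 3.6%. The under-coverage disappears and the interval becomes somewhat conservative overall.

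**Worked example, 34/42 v 2/42.** d = 0.8095 − 0.0476 = 0.7619. Variance = 0.8095 × 0.1905/42 + 0.0476 × 0.9524/42 = 0.00367 + 0.00108 = 0.00475, so the standard error is 0.0689. Wald: 0.7619 ± 1.96 × 0.0689 = 0.627 to 0.897. Miettinen-Nurminen: 0.595 to 0.867.

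**Average shift of the lower limit.** For PASI 75, the Wald lower limit exceeds the Miettinen-Nurminen limit by 3.1, 2.6, 1.8 and 3.7 percentage points on average for Trials 1–4. Average width changes by +0.2, 0.0, −0.6 and +0.6 points (Miettinen-Nurminen minus Wald).

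**The case against.** The strongest reply is that nothing turns on this interval. The Cochran-Mantel-Haenszel test carries the comparison, SAP section 2.6 states that there is no key secondary objective, no margin is attached to the limit, and the lower limit exceeds zero with probability 1.000 to three decimals in every scenario examined. Protocol and SAP agree with each other, and the normal approximation is a conventional companion to the test. All of this stands, and it is why the point ranks low. It does not give the interval its stated level.

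Second, the under-coverage depends on reading the rule as uncorrected. That is the natural reading of the words, but it is an inference. The two readings give materially different intervals, so the choice needs stating either way.

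Third, the 1.8–3.7 point gap is a distance to the Miettinen-Nurminen limit, which is itself slightly conservative on that side (mean error 1.6–1.9% against 2.5%). The gap should therefore not be read as the pure Wald error. This is fair; the error rates measure the defect better than the gap does.

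Fourth, the replacement moves some error to the upper limit and would apply to visits for which no rates are given. Under assumed rates for earlier visits, such as 20% v 1%, the Wald error sits at the upper limit instead (1.7% lower, 5.3% upper, coverage 93.0%). Across the assumed early-visit rates examined (10% v 1% to 40% v 2%), Miettinen-Nurminen coverage averages 94.7–95.5%, but its lower-limit error is 2.6–3.5%, against 0.9–2.6% for Wald. So overall coverage remains close to nominal there, at the price of a somewhat larger lower-limit error.

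**Conclusion.** The concern holds. At the protocol's own Week 12 rates, an uncorrected normal-approximation interval for the PASI 75 difference covers 92.2–93.5% on average over 37–46 per arm (91.3–92.3% at 42). Its lower limit is too high in 4.7–6.8% of trials instead of 2.5%. For IGA 0/1 the shortfall is about one percentage point, and for PASI 90 it is about one point or less.

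This rests on four assumptions: no continuity correction; true rates equal to those observed in the four cited trials, including exactly zero on placebo for Trial 3; independent binomial responses; and arm sizes in the assumed range. The result concerns the accuracy of a reported secondary interval at Week 12. It does not touch the test, the primary endpoint or the efficacy conclusion. The change is optional but worthwhile.

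**What to change.** In SAP sections 2.7.2.2 and 2.7.2.3, replace the normal-approximation interval with the Miettinen-Nurminen score interval for the difference in proportions, and list this in SAP section 4 as a change from protocol section 9.5.1. If the normal approximation is kept, state whether a continuity correction is applied, so that the interval is fully specified.

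The cost is two sentences, one entry in section 4 and a standard software option. Reported Week 12 PASI 75 lower limits become about 2–4 percentage points less favourable, with average width almost unchanged. The replacement is not exact: its mean PASI 75 upper-limit error is 2.9–3.3%, and at 42 per arm with Trial 4 rates it is 4.2%, with coverage of 94.0%.

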#### **2.7.2.3 Investigator's Global Assessment (IGA mod 2011)**

IGA mod 2011 (0 or 1) response will be analyzed at each time point using the Cochran-Mantel-Haenszel test to compare secukinumab and placebo, adjusting for body weight (<90 kg, ≥90 kg). A 95% confidence interval for the difference between the two treatment groups in the proportion of subjects who are responders will be calculated using the normal approximation to the binomial distribution. In addition, the IGA mod 2011 responses by visit will be summarized by treatment.

#### **2.7.2.4 Dermatology Life Quality Index (DLQI)**

Change from baseline in DLQI total score will be analyzed at each time point using the same ANCOVA model as for the primary efficacy variable. In addition, DLQI total score will be summarized by visit and treatment.

### **2.7.3 Handling of missing values/censoring/discontinuations**

For continuous secondary efficacy variables with more than one post-baseline assessment (i.e. cardiometabolic biomarkers and DLQI score), missing data will be imputed using the last-observation-carried-forward (LOCF) method. Baseline value will not be carried forward. If a subject has no post-baseline value, the missing value will not be imputed and the subject will be removed from the analysis.

For the subject who switch treatment after end of treatment period 1 (EOT 1), values of EOT1 are not carried forward to treatment period 2 (EOT 2).

For binary secondary efficacy variables (i.e. PASI 75,90,100 response and IGA mod 2011 0 or 1 response) at Week 12 (and other time points), a subject with a missing assessment will be considered as a responder (yes) if the subject meets the response criterion at the time of premature discontinuation from the study. Otherwise, the subject will be considered as a non-responder (no).

## **2.8 Safety analyses**

Analysis of safety data will be based on the Safety Set.

Any adverse event will be coded using the MedDRA dictionary for the Safety Set.

### **Treatment groups for evaluation**

The summaries of evaluation will be reported for treatment period 1 and entire treatment period, respectively.

The following groups will be used for treatment period 1:

- Secukinumab 300mg
- Placebo

The following groups will be used for entire treatment period:

- Secukinumab 300mg
- Placebo / Secukinumab 300 mg

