3.2 Rationale of study design

The randomized, double-blind, placebo-controlled design used in this study is aligned with the Phase III trials of secukinumab, and with previous studies performed in the indication of chronic plaque psoriasis, and is in accordance with health authority guidelines and feedback, including the United States Food and Drug Administration (FDA).

The study population consists of adult subjects with moderate to severe plaque-type psoriasis who are candidates for systemic therapy or phototherapy.

The primary analysis time point of the trial is at Week 12. This is in line with the timing of the primary analysis time point in the secukinumab Phase III trials, and will allow for assessment of

efficacy at a point in time for which efficacy data from currently approved biologic therapies are available. However, as the study design provides for treatment duration of up to 52 weeks, it also allows for the assessment of longer-term safety and tolerability of secukinumab in this population. For subjects randomized to receive placebo at Visit 2/Baseline, the 52-week treatment duration allows these subjects the opportunity to receive up to 40 weeks of treatment with secukinumab.

Patients with moderate to severe psoriasis have a clinically significant increased risk of major cardiovascular events and mortality independent of traditional risk factors. Treatments that improve not only the skin manifestations of psoriasis but also its cardiovascular co-morbidities are of intense clinical and scientific interest. Measurement of aortic inflammation by FDG-PET/CT is a reproducible, operator independent, prognostic marker of future vascular events (Figueroa et al 2013; Mehta et al 2012). Furthermore, it responds to statins and modulates in a short time frame (i.e., within 12 weeks) unlike alternative approaches such as carotid intima-media thickness (IMT) and MRI-based measures of wall thickness (Tawakol et al 2013).

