### **Secondary objectives**

- To evaluate the effect of secukinumab compared to placebo with respect to change from baseline in cardio metabolic biomarkers (cardio metabolic function [lipid particle size, HDL function (cholesterol efflux)], measures of inflammation [TNF-Alpha, IL-6, C reactive protein, GlycA], adiposity [leptin and adiponectin], insulin resistance [insulin levels/glucose to yield HOMA-IR], and markers predictive of diabetes [apolipoprotein B, ferritin, IL-2 receptor A, IL-18, and fetuin-A]) at Week 12
- To evaluate the effect of secukinumab compared to placebo in subjects with moderate to severe chronic plaque-type psoriasis with respect to change from baseline in the PASI 75, 90 and 100 response rates at Week 12
- To evaluate the effect of secukinumab compared to placebo in subjects with moderate to severe chronic plaque-type psoriasis with respect to the Investigator's Global Assessment mod 2011 (IGA mod 2011) 0 or 1 response at Week 12
- To evaluate the effects of secukinumab compared to placebo with respect to change from baseline in the Dermatology Life Quality Index (DLQI) total score at Week 12

- To evaluate the clinical safety and tolerability of secukinumab as assessed by vital signs, clinical laboratory variables, and adverse event monitoring.

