## **2.2 Analysis sets**

The following analysis sets will be used for the statistical reporting and analyses:

**Randomized Set:** The randomized set includes all subjects who were randomized.

**Safety Set:** The Safety Set includes all subjects who received at least one dose of study medication. Subjects will be analyzed according to treatment received.

**Full Analysis Set:** The Full Analysis Set includes all subjects to whom study medication has been assigned. Subjects inappropriately randomized (e.g., IRT was called in error for randomization of a screen failed subject) will be excluded from this analysis set. Following the intent-to-treat principle, subjects will be analyzed according to the treatment they were assigned to at randomization.

Rule for exclusion criteria from analysis sets: See [Appendix 5-5](#).

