### 5.1 Imputation rules

#### 5.1.1 AE date imputation

The following table explains the notation used in the logic matrix. Please note that **missing start dates** will not be imputed.

	Day	Month	Year
Partial Adverse Event Start Date	Not used	MON	YYYY
Treatment Start Date (TRTSTD)	Not used	TRTM	TRTY

The following matrix explains the logic behind the imputation.

	MON MISSING	MON < TRTM	MON = TRTM	MON > TRTM
YYYY MISSING	NC Uncertain	NC Uncertain	NC Uncertain	NC Uncertain
YYYY < TRTY	(D) Before Treatment Start	(C) Before Treatment Start	(C) Before Treatment Start	(C) Before Treatment Start
YYYY = TRTY	(B) Uncertain	(C) Before Treatment Start	(A) Uncertain	(A) After Treatment Start
YYYY > TRTY	(E) After Treatment Start	(A) After Treatment Start	(A) After Treatment Start	(A) After Treatment Start

The following table is the legend to the logic matrix.

If AE end date is complete and AE end date < Treatment start date or AE end date is partial and AE imputed end date < Treatment start date, then AE start reference = min (informed consent date, earliest visit date from SV) Else if AE end date is partial, AE end date > = Treatment start date or AE is ongoing, then AE start reference = treatment start date.

Relationship	Time imputation	
Before AE start reference	Partial date indicates AE start date prior to AE start reference	
After AE start reference	Partial date indicates AE start date after AE start reference	
Uncertain	Partial date insufficient to determine relationship of AE start date to AE start reference	
Imputation Calculation		
NC/Blank	No convention	
(A)	MAX(01MONYYYY, AE start reference+1 day)	
(B)	AE start reference+1	
(C)	15MONYYYY	
(D)	01JULYYYY	
(E)	01JANYYYY	
Complete date	No date imputation	
If time is captured for the study
 
Case1: if AE start date is not equal to AE start reference then do the following:
 
If minutes missing then AESTMF = M and time is imputed to hh:00
 
If minutes missing then AESTMF = H and time is imputed to 00:00
 
Case2: if AE start date = AE start reference then AESTMF = H and time is imputed to treatment start time + 1 hour

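### No cumulative adverse event, SAE or death table isolates secukinumab-period events in subjects switched from placebo, who carry about 43% of planned secukinumab exposure

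*SAP*

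**What the plan says.** **Reporting periods.** SAP 2.8, under Treatment groups for evaluation: "The summaries of evaluation will be reported for treatment period 1 and entire treatment period, respectively". Period 1 has one column for secukinumab and one for placebo. The entire period has one for secukinumab and one labelled "Placebo / Secukinumab 300 mg". Neither a post-switch period nor a column combining all secukinumab exposure is defined.

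**The switch.** Protocol 5.2: "Beginning at Week 12, all subjects in the placebo group will be switched to treatment with secukinumab 300 mg s.c". Protocol 3.2 adds that "the 52-week treatment duration allows these subjects the opportunity to receive up to 40 weeks of treatment with secukinumab". Allocation is "in a ratio of 1:1, with approximately 42 subjects per group".

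**Counting.** SAP 2.8.1 presents adverse events and SAEs as numbers and percentages, with each subject counted once per preferred term and once per system organ class. Non-serious events are tabulated up to 7 days after the last dose, and SAEs up to 30 days. SAP 2.8.2 summarises deaths by treatment group. SAP 2.8.3 allows worst-value laboratory shifts over the initial or the entire phase only.

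**Objective.** SAP 1.2: "To evaluate the clinical safety and tolerability of secukinumab as assessed by vital signs, clinical laboratory variables, and adverse event monitoring".

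**Exposure.** The prose in SAP 2.4.1 ends exposure at the switch for subjects who switch. The formula beneath it runs from first dose to the earlier of the last visit and last dose plus 84 days, and has no switch term. Protocol 9.3 plans a summary of time on each treatment.

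**The concern.** The safety objective is about secukinumab, and Protocol 3.2 offers the 52-week duration as a way to assess its longer-term safety. Half the randomised subjects have their first secukinumab doses, including the weekly induction doses, after Week 12. In the cumulative tables, their events from that point share a column with their own placebo events.

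A reader of the study report would have an incidence of each term on secukinumab for one arm only. For the other arm the reader would have a sequence incidence that is neither a placebo rate nor a secukinumab rate. The percentages use all subjects in the group (SAP 2.1), so anyone who left during the placebo phase and never took secukinumab stays in that column's denominator.

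**Working it through.** **1. The plan's own figures.** Switch at Week 12, end at Week 52: 52 − 12 = 40 weeks, which reproduces the stated maximum. Group size, with difference 0.15, SD 0.196 and two-sided 0.05: a t-test has power 0.901 at 37 per arm (0.893 at 36). Then 37/0.90 = 41.1, rounded up to 42 per arm, as planned.

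**2. Share of secukinumab exposure after the switch, full completion.**
- Secukinumab arm: 42 × 52 = 2,184 subject-weeks
- Switched subjects: 42 × 40 = 1,680 subject-weeks (about 32 subject-years)
- Share: 1,680/(1,680 + 2,184) = 1,680/3,864 = 40/92 = 43.5%

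**3. Same share on other scales.**
- Non-serious adverse event window (last dose Week 48, plus 7 days = Week 49): (49 − 12)/[(49 − 12) + 49] = 37/86 = 43.0%
- Active doses: switched subjects 4 (Weeks 12 to 15) + 9 (Weeks 16 to 48) = 13; secukinumab arm 6 + 1 + 9 = 16; 13/29 = 44.8%

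**4. Dropout (assumed, since the documents give only an overall 10% loss).** Let period 1 leavers contribute 6 weeks on average and later leavers 20 weeks after Week 12. With p1 and s1 the period 1 dropout in the placebo and secukinumab arms, and d the later dropout in both:
- Switched: P = (1 − p1)[40(1 − d) + 20d]
- Secukinumab arm: S = 6·s1 + (1 − s1)[12 + 40(1 − d) + 20d]
- Share = P/(P + S)

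| p1 | s1 | d | P | S | Share |
|---|---|---|---|---|---|
| 10% | 10% | 0 | 36.0 | 47.4 | 43.2% |
| 10% | 10% | 10% | 34.2 | 45.6 | 42.9% |
| 20% | 5% | 10% | 30.4 | 47.8 | 38.9% |
| 5% | 20% | 10% | 36.1 | 41.2 | 46.7% |

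Setting the 5% to 0% widens the range only slightly: 30.4/80.4 = 37.8% and 38.0/79.2 = 48.0%.

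**5. Placebo share of the mixed column.** 12/52 = 23.1% of planned time.

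**6. Can the post-switch count be recovered by subtraction?** Take a subject with the same preferred term in Week 6 (placebo) and Week 14 (secukinumab). Period 1 counts 1 and the entire period counts 1, so the difference is 0 and the on-drug event is lost. Subtraction therefore gives the subjects whose first occurrence of the term came after the switch, which is a lower bound. The bound is weaker at system organ class and any-event level, where any placebo-phase event in the class hides a later one.

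**7. Denominator.** If the whole 10% loss fell before Week 12, 42 × 0.10 = 4.2, so about 4 of 42 subjects would sit in the column without having taken secukinumab.

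**8. Partial dates (secondary).** In SAP 5.1.1 the start reference for events not ended before treatment is the first-dose date. The formula for a known later month begins "MAX(01MONYYYY, AE start reference+1 day". Week 12 always falls in a later calendar month than first dose, so an event with the day missing in the switch month is set to the 1st. That is placebo time unless the switch was itself on the 1st. Attribution at onset would inherit this one-directional error.

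**The case against.** The strongest reply is that post-switch data are reported elsewhere. Laboratory and vital-sign changes are summarised by visit (SAP 2.8.3, 2.8.4.2), the protocol summarises exposure by treatment, and adverse event details and all SAEs are listed. SAP 2.4.1.1 provides for period in the safety listings. All of this stands. A reader might infer that 43% of secukinumab exposure goes unreported, and the documents do not support that. The gap is confined to cumulative summaries. Listings of 84 subjects allow a reader to find events, but they do not give an incidence.

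Subtraction also recovers something: a lower bound by preferred term, with disposition by study period as a rough denominator. For deaths the count-once problem does not arise, so what is missing there is attribution and a proper denominator.

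Three further inferences should be resisted:

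- **That the SAP breaks its Safety Set rule.** "Subjects will be analyzed according to treatment received" assigns subjects, not events. A switched subject did receive placebo and then secukinumab, and the column label says so.
- **That 52 and 40 weeks on drug are formally compared by crude percentages.** No between-arm test of adverse events is planned, and both columns cover the same planned follow-up.
- **That undated events are pushed into placebo time.** SAP 5.1.1 does not impute missing start dates. The point concerns partial dates, here a known month with the day missing, and probably few records. It also leaves the entire-period column unchanged, since that column counts both phases.

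**Conclusion.** The point holds in this limited form. The planned cumulative adverse event, SAE and death tables, and the entire-period worst-value laboratory shifts and notable-value counts, do not isolate secukinumab-period events in switched subjects. The share of planned secukinumab exposure affected is 43.5% with full completion, 43.0% on the non-serious adverse event window, and about 39% to 47% with 5% dropout in one arm and 20% in the other before Week 12. The dropout rates and average weeks on treatment are my assumptions; the equal-dropout cases stay near 43%.

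This is a weakness in descriptive reporting of a secondary objective. The primary endpoint and the period 1 comparison groups are unaffected. The one possible leak is a day-missing event moved back across the switch into the period 1 placebo column at the final analysis. The change is worth making because it is cheap and lets the tables answer the stated safety objective.

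**What to change.** In SAP 2.8:

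1. Attribute each adverse event, SAE and death to the treatment taken at onset.
2. Add an *Any secukinumab* column covering both arms from the first secukinumab dose, with the denominator limited to subjects who received it, and give exposure-adjusted incidence beside the percentages. Apply the same column to entire-period worst-value shifts and notable-value counts.
3. Keep the period 1 tables as they are.

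In SAP 2.4.1, reconcile the prose, which ends exposure at the switch, with the formula, which does not. Exposure-adjusted incidence needs this settled first.

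In SAP 5.1.1, for switched subjects, impute day-missing start dates in the switch month against the switch date.

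No new data are needed. The cost is SAP wording, a derived switch date, new denominators and extra table programming, which is somewhat more than one added column.
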